9.4 Sample Size Justification

The dose escalation portion of this study is a modified 3+3 design with no dose de-escalation. The sequential cohort enrollment characteristics of this design do not allow a fixed computation of sample size. The parameters of the design that can be calculated are shown in [Table 4](#). Based on an assumed vector of probabilities of any pharmacologic activity or an ADR for a subject, the probability of each dose being the MTD is shown in the table. The average sample size of the dose escalation phase of the study is $n=26.3$ patients for the assumed vector of probabilities of any pharmacologic activity or an ADR.

Table 4. Design Characteristics for the Study Design

Dose Group	1	2	3	4	5	6	7	8	9	Total
Assumed Probability of any pharmacologic activity or a ADR for a subject	.01	.02	.05	.08	.10	.13	.16	.19	.22	---
Probability of the Dose Being the MTD	.002	.012	.039	.071	.103	.136	.152	.148	.065	---
Average Sample Size for Each Dose and Total	3.1	3.2	3.4	3.5	3.3	3.2	2.8	2.2	1.6	26.3

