3.2 Justification for Study Design and Population

This study is designed to evaluate the safety and tolerability of escalating doses of Tc 99m tilmanocept. Whole body planar as well as a planar scan of the hands using a SPECT camera will also be combined with 3D SPECT or SPECT/CT imaging to provide greater resolution of areas of Tc 99m tilmanocept localization. Additionally, the PK and dosimetry of the MTD of Tc 99m tilmanocept will be evaluated in twelve subjects from Groups 10 and 11. Planar gamma camera imaging will be used to assess dosimetry.

This study is designed to evaluate the use of Tc 99m tilmanocept as an imaging agent in subjects with known active rheumatoid arthritis by evaluating the localization in inflamed joints.

No clinical trials have been conducted to evaluate IV administration of Tc 99m tilmanocept performance in subjects with rheumatoid arthritis. The rationale for evaluating Tc 99m tilmanocept in this subject population is discussed in [Section 1.1](#) and [Section 1.2](#).

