5.3 Treatment Assignment

In this open-label, non-randomized, multicenter, dose-escalation safety study all subjects will receive IV administration at one of 3 tilmanocept mass doses: 50 µg, 200 µg, or 400 µg. Within each mass dose group, subjects will receive tilmanocept labeled to one of 3 radiolabel Tc 99m doses: 1 mCi, 5 mCi, or 10 mCi.

Group 1 will be the starting dose group. Three subjects will be enrolled into Group 1. If none of the 3 subjects experiences pharmacologic activity or an ADR, 3 subjects will be enrolled in Group 2. However, if one of the first three subjects experiences a pharmacologic activity or an ADR, three more subjects will be treated at the same dose level. If 2 out of 3 or 3 out of 6 subjects experiences a pharmacologic activity or an ADR in Group 1 the MTD cannot be determined. If no additional pharmacologic activity or ADRs are observed in the expanded group, the dose escalation will continue. If one additional pharmacologic activity or ADR is observed, the current dose will be deemed the maximum tolerated dose (MTD). If more than one additional pharmacologic activity or ADR is observed in the expanded group, the previous dose will be deemed the MTD. Dose escalation will continue until the MTD is found or until Group 9 is reached with only one ADR or without any ADRs. If no ADRs are experienced from Groups 1-9, then the MTD will be highest tilmanocept mass dose radiolabeled at the highest level (400 µg/10 mCi).

Group 10 will consist of 6 HC subjects and Group 11 will consist of 6 subjects with active RA. Subjects enrolled in Groups 10 and 11 will be dosed at the dose level that is established as the MTD from Groups 1 through 9. The maximum tolerated dose is defined as the dose below where >33% of subjects experienced an ADR.

NOTE: Adverse Drug Reaction

An Adverse drug reaction (ADR) includes all noxious and unintended responses to a medicinal product related to any dose or dose regimen. The phrase “responses to a medicinal product” means that a casual relationship between a medicinal product and an adverse event is at least a reasonable possibility, i.e. the relationship cannot be ruled out.

In this multi-center trial, doses will be serially assigned in an open label fashion in accordance with [Table 1](#). Investigators who have identified a subject for participation will receive the dose assignment from the sponsor and request that dose from the supporting Cardinal Health pharmacy.

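### Table 4 assigns risk by group number although Table 1 lowers both mass and activity at Groups 4 and 7, so its MTD probabilities (0.152 for the lowest dose) do not apply to this dose order

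*Combined protocol and SAP*

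**What the plan says.** Table 1 (Section 5.2) sets Groups 1-3 at 10 mCi, Groups 4-6 at 5 mCi and Groups 7-9 at 1 mCi. Within each triplet the mass dose is 50, 200 and 400 µg. Section 5.3 starts at Group 1, runs to Group 9, and says that "doses will be serially assigned in an open label fashion in accordance with" this matrix.

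The rules in Section 5.3 are:
- No event in 3 subjects, or 1 in 6: escalate.
- One additional event in the expanded group: the current dose is the MTD.
- "If more than one additional pharmacologic activity or ADR is observed in the expanded group, the previous dose will be deemed the MTD".
- For two or more events in a first cohort of three, a consequence is written for Group 1 only. That sentence covers 2/3 and 3/6 and reads in part: "subjects experiences a pharmacologic activity or an ADR in Group 1 the MTD cannot be determined".
- Where no ADR occurs in any group, "then the MTD will be highest tilmanocept mass dose radiolabeled at the highest level", that is 400 µg/10 mCi, which is Group 3.

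The same section adds a definition: "The maximum tolerated dose is defined as the dose below where >33% of subjects experienced an ADR".

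Table 4 (Section 9.4) has a row labelled "Assumed Probability of any pharmacologic activity or a ADR for a subject", which holds the values .01, .02, .05, .08, .10, .13, .16, .19 and .22 for Groups 1-9. It reports MTD probabilities of .002, .012, .039, .071, .103, .136, .152, .148 and .065, and an average of 26.3 subjects. The synopsis repeats 26.3 and the 0.152 for Group 7.

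**The concern.** Going from Group 3 to 4, the dose drops from 400 µg/10 mCi to 50 µg/5 mCi. Going from Group 6 to 7, it drops from 400 µg/5 mCi to 50 µg/1 mCi. Table 4 raises the assumed risk at both steps, from .05 to .08 and from .13 to .16. The documents give no reason why risk should rise when mass and activity both fall, and Section 5.3 itself treats 400 µg/10 mCi as the top dose. A reader of the synopsis is told that the lowest of the nine doses has the largest chance of being the MTD.

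Finding the MTD is the stated statistical objective (Section 9), and Table 4 is the only quantitative support for the escalation design. The MTD also sets the dose for the later cohorts: Groups 10 and 11 "will be dosed at the dose level that is established as the MTD from Groups 1 through 9". Those are twelve subjects, six of them healthy controls.

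**Working it through.** **Inputs.** The group order is from Table 1, the rules from Section 5.3, and the risk vector and printed results from Table 4.

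**Formulas.** For event probability p in a group, let a = (1−p)³ and b = 3p(1−p)².
- Escalate (0/3 or 1/6): E = a(1+b)
- Current group is MTD (2/6): C = b²
- Fail (2/3, 3/3, or more than one additional event): F = (1−a−b)(1+b); the previous group is MTD
- Expected subjects in a group that is reached: 3+3b

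With Rⱼ the product of E over Groups 1 to j−1, P(Group j = MTD) = RⱼCⱼ + Rⱼ₊₁Fⱼ₊₁. Sending 2/3 or 3/3 to the previous group is inferred from Table 4, because the text gives that rule only for Group 1.

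**Reproducing Table 4.** For Group 7, p = .16 gives a = .5927, b = .3387 and C = .1147. For Group 8, p = .19 gives F = .1300. With R₇ = .7008 and R₈ = .5560:

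.7008 × .1147 + .5560 × .1300 = .0804 + .0723 = .153 (printed .152)

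The full row is .002 .012 .039 .071 .103 .136 .153 .148 .065, and expected N is 26.5 (printed 26.3). If 2/3 or 3/3 in a first cohort did not point to the previous group, Group 7 would be .100, which does not match. So Table 4 is computed correctly for nine steps of rising risk. The printed row sums to .728. The remainder is .270 for clearing all nine groups and .0003 for failing at Group 1.

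**Same rules and group order, with risk that does not fall as mass or activity rises.**

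| Assumed risk, Groups 1-9 | P(Group 7 = MTD) | Expected N |
|---|---|---|
| Table 4 as printed | 0.152 | 26.3 |
| Table 4 values sorted by mass, then activity: .05 .13 .22 .02 .10 .19 .01 .08 .16 | 0.008 | 20.3 |
| Table 4 values sorted by activity, then mass: .16 .19 .22 .08 .10 .13 .01 .02 .05 | 0.001 | 16.4 |
| All 42 dose-consistent orders of Table 4's values | 0.001-0.008 | 16.4-20.3 |
| .01/.02/.05 by mass at each activity (assumed) | 0.002 | 28.0 |
| Nine assumed mass-only vectors, from .01/.02/.05 to .16/.19/.22 | not tabulated | 14.9-28.0 |

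**Upper bound for Group 7.** A numerical search over vectors non-decreasing in mass and activity found the maximum at flat risk of about .123. There E = .8660, C = .0805 and F = .0535:

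.8660⁶ × .0805 + .8660⁷ × .0535 = .0339 + .0195 = .0535

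The printed value is 0.152/0.0535 = 2.8 times this maximum.

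**Secondary point: the previous dose at Groups 4 and 7.** After failure at Group 4 the rule names Group 3, and after failure at Group 7 it names Group 6. Each has 400/50 = 8 times the mass of the group that failed, and more activity. Each has also already passed with 0/3 or 1/6. Neither is a dose below the failing one. The probability of this outcome is R₄F₄ + R₇F₇. Over the 42 orders it is 0.06%-1.05%, including the inferred first-cohort rule. The written expanded-group sentence alone accounts for 0.003%-0.18%.

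**The case against.** The strongest defence is that Table 4 is labelled as an assumption, its arithmetic reproduces, and little depends on it. Section 9.4 says that no fixed sample size can be computed. The cap of 36 subjects for Groups 1-9 (Section 8.1.1) does not come from 26.3, and no stopping rule or dose assignment uses 0.152. All of that stands, and it limits the point to a planning table. It does not rescue the printed probabilities, because the assumption runs against the dose order in Table 1.

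Four stronger readings are tempting but not supported:
- A reader might infer that 26.3 is wrong. It lies inside the 14.9-28.0 range from the mass-only vectors.
- A reader might infer that Groups 10-11 could receive a dose that failed. The dose named at Groups 4 and 7 has always cleared. Because escalation runs in group order, the dose below could also be read as the preceding step, so this is a poor fit with the definition rather than a proven contradiction.
- A reader might run Table 4's own vector through the rule and conclude that a higher dose is named in 8.6% of trials. Under that vector the previous group carries the lower risk (.05 against .08, .13 against .16), so the figure does not measure harm. Of its .0855, .0657 comes from the unwritten first-cohort rule.
- A reader might infer that a failure at Group 4 or 7 must suspend Groups 10-11 until an amendment. Giving up a cleared dose in favour of a hold is a preference.

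It can also be said that a larger gap lies elsewhere. With .01/.02/.05 at each activity, all nine groups clear in .907 of trials, but no event at all occurs in (.99 × .98 × .95)⁹ = .480. The other .907 − .480 = .427 clear with at least one event, and the clause for no ADRs does not name their MTD. That is a fair observation and a separate matter.

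**Conclusion.** The concern holds for Table 4's MTD probabilities. They describe a ladder in which risk rises with every group number, which Table 1 is not. The conclusion rests on one premise: risk does not fall as mass or activity rises. That is the usual basis for an MTD and agrees with how Section 5.3 ranks 400 µg/10 mCi. The expected N depends on the vector chosen and is simply unsupported for this order. The difficulty with the previous-dose rule is real as wording but rare under dose-ordered risk. This should be fixed as a misleading operating characteristic. It is not an error in trial conduct.

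**What to change.** 1. Recompute Table 4, and the 26.3 and 0.152 quoted in Section 9.4 and the synopsis, with a risk vector that is non-decreasing in mass and activity. State the vector and the reason for it. The .01/.02/.05 vector in the table above is one example, not a recommendation.
2. Add a column for clearing all nine groups: .907 with that example, .270 with Table 4's values.
3. In Section 5.3, refer to the next lower dose (the next lower mass at the same radiolabel level) in place of the previous dose, and state the rule for 2/3 or 3/3 in a first cohort beyond Group 1. Say explicitly what follows a failure at Group 4 or 7, since no lower mass exists there. Retaining cleared Group 3 or 6, or holding Groups 10-11, is the sponsor's choice.

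The cost is a recalculated table and a few sentences. Group order, stopping points, the 2/6 rule and patient numbers do not change. If the sponsor chose a hold, the PK and dosimetry cohorts would have no dose until one was set. Under the example vector that arises in about 0.06% of trials.

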9.5 Statistical Analyses

9.5.1 Analysis Populations

The following analysis population will be defined for the study:

- **Intent-to-Diagnose (ITD) Population** - Subjects who are enrolled in the study in Groups 1-9, injected with Tc 99m tilmanocept, and received whole body planar imaging will be included in the ITD analysis population.
- **Radiopharmacokinetic (RPK) Population** – Subjects that have been enrolled in the study in Groups 10-11, injected with Tc 99m tilmanocept, and received whole body planar imaging will be included in the RPK analysis population.
- **Safety Population** – All patients who are enrolled and injected with Tc 99m tilmanocept in the study will be included in the safety population.
- **Per Protocol (PP) Population** – The PP population will include all safety subjects without major protocol violations.

All safety data analyses will be conducted on the safety population. All efficacy data analyses will be conducted on the ITD and PP population with the ITD population being the primary analysis set. All analyses of RPK data will be carried out on the RPK population.

9.5.2 Analysis of Baseline and Demographic Characteristics

The distribution of each baseline and demographic variable of interest will be summarized by dose group. Continuous variables will be summarized via mean, median, standard deviation, and range. Categorical variables will be summarized via counts and percentages.

9.5.3 Analysis of Efficacy Variables

Per subject localization rates and percentage will be calculated by imaging time point by dose group and overall.

Per joint location localization rates and percentages will be calculated by time point by dose group and overall.

Per location concordance of clinical diagnosis to nuclear medicine specialist illumination indication will be computed across all RA positive sites of all subjects at all time points.

Localization intensities will be summarized by descriptive statistics (mean, median, standard deviation, minimum, maximum and range) by joint location at each time point.

Other efficacy analyses will be described in the Statistical Analysis Plan (SAP) for the study.

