3 OVERVIEW OF METHODOLOGY AND DESIGN

3.1 Overall Study Design

Prospective, open-label, multicenter, dose escalation, and safety with PK and dosimetry study of injected Tc 99m tilmanocept in the detection of and assessment of localization to skeletal joints in subjects with and without active RA by SPECT imaging. Subjects will receive IV administration at one of 3 mass doses: 50 µg, 200 µg, or 400 µg. Within each mass dose group, subjects will receive Tc 99m tilmanocept labeled with one of 3 radiolabel doses: 1 mCi, 5 mCi, or 10 mCi. All subjects will have a whole body planar SPECT scan. Subjects enrolled in Groups 1-9 will receive a whole body planar SPECT scan and planar of hands at two specified time points: 60 minutes ± 15 minutes, and 180 minutes ± 15 minutes followed by a 3D SPECT or SPECT/CT scan on areas of interest. Subjects enrolled in Groups 10-11 will have a whole body planar SPECT scan with pharmacokinetic and dosimetry tests performed at 4 specified time points post injection: 15 ± 5 minutes, 60 ± 15 minutes, 180 ± 15 minutes, and 18-20 hours. Subjects enrolled in Groups 10-11 will also receive a planar SPECT hands scan at 60 ± 15 minutes and 180 ± 15 minutes post-injection. PK blood sampling will be performed before injection (within 15 minutes), immediately following injection (within 5 minutes), and at each scanning timepoint. Dosimetry tests will be performed at each scanning timepoint. PK of urine will be assessed through counts of the bladder wall obtained from cumulative quantitative planar imaging from radiation dosimetry. The proposed study includes 3 visits: A screening visit for initial determination of eligibility and evaluation of clinical status (Visit 1), a baseline: Day 1 (Visit 2) on the day of tilmanocept administration and imaging, and a safety follow-up (Visit 3).

The Schedule of Events ([Appendix 1](#)) contains a list of all study procedures and time points. Study activities are described in detail in [Section 7](#).

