9.3 Efficacy Variables

The efficacy variables for this study are as follows:

- Nuclear medicine specialist qualitative determination of presence/absence of radiotracer uptake (i.e., Tc 99m tilmanocept localization positive/negative) relative to background from SPECT imaging results for each DAS28 joint location for each subject (deemed the “gold standard” result, 28 joint locations per subject)
 - Clinically identified presence/absence of RA using the DAS28 instrument (28 joint locations per subject)
- Quantitative planar imaging intensity of radiotracer uptake for each joint location

A location/joint would be considered clinically identified as RA positive if it is either swollen or tender as measured by the DAS28 instrument. The presence of radiotracer uptake relative to background as determined by the nuclear medicine specialist at a location would indicate the location is RA positive.

The efficacy endpoints for this study are as follows:

- Per subject localization rate of Tc 99m tilmanocept by SPECT imaging
- Per joint location clinically RA-identified joint localization rate of Tc 99m tilmanocept by SPECT imaging

- Concordance of Tc 99m localization with anatomical areas of active RA defined by clinical symptomology.
- Localization intensity for each clinically RA-defined joint (as determined by quantitative SPECT gamma counts)
- Per subject localization rate of Tc 99m tilmanocept in areas other than RA-positive joints by SPECT imaging
- The following PK parameters will be calculated for each subject, whenever possible, using Tc 99m tilmanocept total radioactivity in whole blood and urine: maximum observed concentration (C_{max}), time to C_{max} (t_{max}), area under the concentration-time curve (AUC) from Hour 0 to the last measureable concentration (AUC_{0-t}), AUC extrapolated to infinity ($AUC_{0-\infty}$), apparent terminal elimination rate constant (λ_z), and apparent terminal elimination half-life ($t_{1/2}$).
- Radiation dosimetry of Tc 99m tilmanocept will include radiation doses per organ ($\mu\text{Gy}/\text{MBq}$), organs receiving the highest organ dose (HT), effective doses per organ ($\mu\text{Sv}/\text{MBq}$), mean effective dose ($\mu\text{Sv}/\text{MBq}$), effective dose resulting from a diagnostic dose $\pm 20\%$. Dosimetry will be based on target organ image counts and modeling per OLINDA/EXM® 2.0 software.

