Per subject localization of Tc99m by SPECT imaging is defined as the illumination of at least one site relative to background in a subject as determined by the nuclear medicine specialist.

Per joint location RA-identified localization rate is the number of joint locations that are clinically RA positive and SPECT illuminated divided by the total number of joints.

Per joint location concordance of Tc99m localization to clinically positive RA joints is the number of joint locations that are clinically RA positive and SPECT illuminated divided by the number of clinically RA positive joints.

Per subject localization rate of Tc99m by SPECT imaging in areas other than RA-positive joints is defined as the illumination of at least one joint location relative to background that is clinically RA negative in a subject divided by the number of subjects.

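### Concordance is planned as a single figure over all doses and imaging times, so this secondary endpoint cannot be read by dose or by time

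*Combined protocol and SAP*

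**What the plan says.** Section 9.3 defines per-joint concordance as "the number of joint locations that are clinically RA positive and SPECT illuminated divided by the number of clinically RA positive joints". The unit is a joint location, and the definition carries no time index. The neighbouring per-joint localization rate has the same numerator but is "divided by the total number of joints".

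Section 9.5.3 then sets out four summaries:

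- **Per-subject localization rate:** by imaging time point, by dose group and overall.
- **Per-joint localization rate:** "Per joint location localization rates and percentages will be calculated by time point by dose group and overall".
- **Localization intensity:** "by joint location at each time point", with no dose split.
- **Concordance:** it "will be computed across all RA positive sites of all subjects at all time points", with neither split. The synopsis uses the same words.

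Groups 1-9, the primary efficacy set (ITD, section 9.5.1), are imaged "at two specified time points: 60 minutes ± 15 minutes, and 180 minutes ± 15 minutes" (section 3.1). DAS28 joint status is recorded once, at screening (section 8.1.3). Section 9.5.5 requires both an image value and a clinical value for a joint to be used. It gives no rule for combining two image readings of the same joint.

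**The concern.** Agreement between localization and clinical symptoms is part of the first secondary objective and is a listed secondary endpoint. A single figure over all subjects and times has three weaknesses as a description.

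1. **Time.** One clinical reading is paired with two image readings, although the definition in 9.3 counts joints. The result is an average over 60 and 180 minutes and describes neither.
2. **Dose.** The figure averages nine combinations, from 50 to 400 µg and from 1 to 10 mCi. The weights depend on how many positive joints each subject has and on which cohorts were expanded from 3 to 6 after a safety event (section 5.3). Neither has to do with imaging performance.
3. **Denominator wording.** Section 9.5.3 speaks only of RA positive sites. Section 9.3 uses the term RA positive both for clinically swollen or tender joints and for uptake, which "as determined by the nuclear medicine specialist at a location would indicate the location is RA positive". The endpoint definition does settle the denominator, "divided by the number of clinically RA positive joints", but the analysis sentence does not repeat it.

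At stake is whether a reader of the results can say how well the image agrees with the clinical examination at a given dose and imaging time.

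**Working it through.** The documents give no expected value, sample size or precision for concordance, so there is no stated figure to reproduce. Table 4 concerns dose escalation only.

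**Inputs from the documents.** 28 joints per subject (9.3); 9 dose cells of 3 subjects, so 27 before expansion (Table 1); up to 36 subjects in Groups 1-9 (8.1.1); 2 imaging times (3.1); 1 clinical reading (8.1.3).

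**Assumed.** Clinically positive joints per subject m = 6, 10 or 14; correlation ρ between the two readings of one joint = 0.5, 0.7 or 0.9. The documents give neither.

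**Step 1: joints against readings.**
- All DAS28 joints: 27 × 28 = 756 joints, × 2 = 1,512 readings. With 36 subjects: 1,008 and 2,016.
- Clinically positive joints, 27 subjects: 27m = 162, 270 or 378 joints, giving 324, 540 or 756 readings.

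**Step 2: effect on the point estimate.** If every joint is read at both times, the pooled proportion is the plain average of the 60- and 180-minute proportions. Duplication alone introduces no bias. If one scan of a joint is missing and records are simply stacked, that joint carries half the weight of the others.

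**Step 3: what the average can hide (invented values).** Suppose concordance at 60/180 minutes is 35/45%, 60/70% and 75/85% for the three mass doses, with equal numbers of positive joints. The pooled figure is (35 + 45 + 60 + 70 + 75 + 85)/6 = 61.7%. The split would show 40, 65 and 80% by mass dose, and 56.7 against 66.7% by time.

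**Step 4: weights.** With equal joint counts, an unexpanded cell has weight 3/27 = 11%. If one cell expands to 6, its weight is 6/30 = 20% and every other cell falls to 3/30 = 10%.

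**Step 5: does the split localization rate stand in?** With perfect concordance, a subject with 6 positive joints has a localization rate of 6/28 = 21%, and one with 14 has 14/28 = 50%. At identical agreement the rate differs more than twofold, purely with disease burden.

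**Step 6: precision, only if an interval were added later.** Two readings of one joint carry the information of 2/(1+ρ) readings: 1.33, 1.18 and 1.05. A standard error that treats them as independent is 1/√(1+ρ) of the true one: 0.82, 0.77 and 0.73. Adding correlation c between joints of one subject, the design effect is (1+ρ) + (2m−2)c. With m = 10 and ρ = 0.7 it is 1.7 + 18c, that is 2.6, 3.5 and 7.1 at c = 0.05, 0.1 and 0.3. The true standard error is then 1.6, 1.9 and 2.7 times the naive one.

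**Step 7: what the split leaves.** 9 × 2 = 18 cells. Each has 3 subjects and 18, 30 or 42 positive joints. By mass dose, 9 subjects give 54, 90 or 126 positive joints per time point.

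**The case against.** **The time wording is open.** At all time points could mean at each of them, and no text describes stacking records. This stands in part. The same section writes by time point or at each time point when it means that, so pooling is the more natural reading. The missing dose split does not depend on the answer.

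**Intensity has no dose split either.** True. Concordance is not the only summary pooled over dose; it is the only one of the four with neither split.

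**The localization rate already shows a gradient in the shared numerator.** It would show one, but mixed with the number of positive joints per subject (step 5). In 3-subject cells that mixing cannot be ignored.

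**Further efficacy analyses are deferred to a statistical analysis plan.** The deferral in 9.5.3 covers other analyses. Concordance is already specified there, and the text reviewed holds no further rule for it.

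**Stronger readings that the documents do not support.**
- A reader might infer that concordance is 100% by construction, because uptake makes a location RA positive. It is not: 9.3 fixes both the numerator and the clinical denominator. Even with an uptake denominator, the ratio would be the share of illuminated joints that are clinically positive, a predictive value.
- A reader might infer that pooling removes the basis for choosing dose and imaging time. Section 2.2 ties that choice to localization intensity, not concordance.
- A reader might infer that the plan reports intervals that are too narrow. No interval or test is planned for concordance, so step 6 is conditional.

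**Conclusion.** The point holds as a cheap improvement to a descriptive secondary endpoint. As written, concordance is one figure that mixes nine dose combinations and, on the plain reading, enters each positive joint in Groups 1-9 twice against one clinical status. It cannot be interpreted by dose or imaging time, and no other planned output supplies that information.

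The harm goes no further than this. The estimate is unbiased for the two-time average when both scans are read, and neither the safety conclusions nor the planned basis for dose selection is affected.

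The number of positive joints per subject, the correlations and the concordance values in the example are assumptions; the missing splits are in the text. The count of two applies to the ITD set. The per-protocol set is drawn from all safety subjects and could include Group 11, which is scanned at four times, so a joint could enter up to four times there.

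**What to change.** In section 9.5.3 and the synopsis, replace the concordance sentence with wording to this effect: *Per-joint concordance, with numerator and denominator as defined in section 9.3, is computed separately at each imaging time point, by dose group and overall; each joint is counted once per time point.*

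In the same sentence, name the denominator as clinically RA positive (DAS28) joints instead of RA positive sites.

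Add that any interval placed on the overall figure must account for joints clustered within subjects. Intervals by dose group are not requested: with 3 subjects there are only C(5,3) = 10 distinct subject-level resamples.

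The cost is a wording change and a few more table rows, with no new data. The downside is that dose-group cells of about 3 subjects will be imprecise. They should be labelled descriptive, as the localization rates already split this way should be.
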